6. PRIOR AND CONCOMITANT THERAPY

Any medication or vaccine (including over-the-counter and prescription medicines, vitamins, and/or herbal supplements) that the patient is receiving within 30 days before the first dose of dinutuximab beta:

- Reason for use
- Dates of administration including start and end dates
- Dosage information including dose and frequency

The Medical Monitor should be contacted if there are any questions regarding concomitant or prior therapy.

6.1. Premedication

Antihistamine premedication (eg, diphenhydramine) should be administered by intravenous injection approximately 20 minutes or orally based on the physician's judgment before starting each dinutuximab beta infusion. It is recommended that antihistamine administration be repeated every 4 to 6 hours as required during dinutuximab beta infusion.

Patients should be closely monitored for anaphylaxis and allergic reactions, particularly during the first and second treatment course.

Pain

Neuropathic pain usually occurs at the beginning of the treatment and premedication with analgesics, including intravenous opioids, before each infusion of dinutuximab beta is required. A triple therapy including nonopioid analgesics (according to World Health Organization guidelines), gabapentin, and opioids is recommended for pain treatment. The individual dose may vary widely.

Nonopioid analgesics

Nonopioid analysesics should be used permanently during the treatment, eg, paracetamol or ibuprofen (refer to local label for details regarding administration).

Gabapentin

The patient should be primed with 10 mg/kg/day, starting 3 days before dinutuximab beta infusion. The daily dose of gabapentin is increased to 2 x 10 mg/kg/day orally the next day and to 3 x 10 mg/kg/day orally the day before the onset of dinutuximab beta infusion and thereafter. The maximum single dose of gabapentin is 300 mg. This dosing schedule should be maintained as long as required by the patient.

Oral gabapentin should be tapered off after weaning off intravenous morphine infusion at the latest after dinutuximab beta infusion therapy has been stopped.

6.2. Continuous Morphine Infusion Schedule

Opioids are the standard pain treatment given alongside dinutuximab beta to prevent severe visceral and neuropathic pain. The amount of opioid required in the continuous infusion setting

is less than that in the short-term infusion setting. The first day and cycle usually requires more amount of opioid than subsequent days and cycles. Opioids should therefore be started and then gradually weaned off according to the needs of the patient. Except for respiratory depression and sedation, the AEs in children and in adults are essentially the same (nausea, vomiting, constipation, pruritus, urinary retention, and lowered seizure threshold). The safety and efficacy of continuous intravenous administration of opioids for pain management are well established for all age groups. The risk of dependence is classified as low.

Tramadol should be used for moderate to severe pain, but for severe to very severe pain, morphine is preferred unless it is poorly tolerated by certain individuals, in which case other opioids can be used.

During the first cycle, intravenous morphine should initially be given as follows:

A morphine sulphate bolus (0.02 to 0.05 mg/kg/h) should be administered before the start of continuous infusion of dinutuximab beta. Thereafter, it is recommended to administer morphine sulphate at a continuous infusion rate of 0.03 mg/kg/h on the first day. The morphine dose can ideally be tapered on a daily basis over the first 5 days (to 0.02 mg/kg/h to 0.01 mg/kg/h to 0.005 mg/kg/h). Boluses can be either self-administered or administered by a nurse at 0.02 mg/kg/dose. If continuous morphine is required for > 5 days, the dose should be decreased at the end of treatment by 20% each day. It is expected that intravenous morphine can be rapidly tapered off. Depending on the individual patient's pain tolerance, subsequent cycles can be started with intravenous morphine, including the bolus loading dose, and tapered until a safe and well-tolerated outpatient pain management regimen is in place; for example,

- Oral morphine: administered at a dose of 0.2 to 0.4 mg/kg every 4 to 6 hours
- Oral tramadol: if pain is well-controlled on low doses of oral morphine
- Transdermal fentanyl patches: in centers where these are used regularly for pain control. The equivalent morphine to transdermal fentanyl dose rate in µg/h will be calculated based on the current use of intravenous morphine according to the manufacturers guidance and the dose will be gradually decreased according to pain symptoms.

The use of long-acting morphine is not recommended in this situation as it takes 48 hours to stabilize the dose, which is not practical.

6.3. Prohibited Concomitant Medications

The following medications are prohibited during the study or as otherwise noted:

- Any chemotherapy, hormonal anticancer therapy, radiotherapy, or experimental
 anticancer medications other than those that are study related, until patients have
 completed end of study assessments at the Safety Follow-up Visit or have
 discontinued study drug with dinutuximab beta prematurely
- Systemic glucocorticoids or other drugs with known immunosuppressive activity within 2 weeks of starting and 1 week after completing treatment with dinutuximab beta except to treat life-threatening conditions

- The use of intravenous immunoglobulin (IVIG), because IVIG may interfere with the dinutuximab beta-mediated antibody-dependent cellular cytotoxicity, within 2 weeks of starting and 1 week after completing treatment with dinutuximab beta
- Tetracycline is prohibited when the patient is taking 13-cis-RA

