- AEs will be characterized by type, frequency, severity (as graded by the NCI CTCAE version 5.0), timing, seriousness, and relationship to study drug will be recorded; other safety assessments to be performed including vital signs, physical examinations, ophthalmologic examination, performance status, laboratory safety tests, etc.
- Blood samples will be collected on Day 1, 3, 8, 11, 15 (optional), 22 (optional), and 29 in Cycle 1, and on Day 1 and 11 in Cycle 2, 3, and 4 to characterize the PK of dinutuximab beta.
- Tumor assessments or monitoring will be performed by the investigators at Screening Visit, end of treatment Cycle 3, and end of treatment visit. International Neuroblastoma Response Criteria (INRC) (Brodeur et al 1993) is recommended as a reference for response evaluation in patients evaluable for tumor assessment.

Duration of Patient Participation:

Patients will receive study drugs until the completion of the 5 treatment cycles (ie. 25 weeks), tumor relapse, progressive disease (PD), unacceptable toxicity, death, or other discontinuation criterion is met.

Study Population:

Patients aged \geq 12 months with high-risk neuroblastoma who have previously received induction chemotherapy and achieved at least a partial response followed by myeloablative therapy and stem cell transplantation

Key Eligibility Criteria:

- Patients aged ≥ 12 months
- Diagnosis of high-risk neuroblastoma according to the International Neuroblastoma Staging System (INSS) criteria, ie, INSS Stage 4 without *MYCN* amplification (MNA) and aged ≥ 18 months; or INSS Stage 2-4 with MNA
- Patients who have previously received induction chemotherapy and achieved a partial or complete response followed by myeloablative therapy and stem cell transplantation

Investigational Products, Dose, and Mode of Administration:

Dinutuximab beta

- Dinutuximab beta at 100 mg/m²/cycle will be given as continuous long-term infusion (LTI) for 10 days from Day 1 to Day 11 in every 35-day cycle.
- Up to 5 cycles of infusion will be administered.

13-cis-RA

- 13-cis-RA will be given orally at a dose of 160 mg/m²/day, divided into close to 2 equal doses twice a day for 14 days, started on the next day after completion of dinutuximab beta infusion.
- Up to 5 cycles of oral administration will be applied.

Reference Therapy, Dose, and Mode of Administration:

Not applicable

Statistical Methods:

Analysis Sets

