7.6. Discontinuation From Study Treatment or From the Study

7.6.1. Patient Discontinuation From Study Treatment (End of Treatment for an Individual Patient)

Patients have the right to discontinue study drug at any time for any reason. In addition, the investigator has the right to discontinue a patient from study drug at any time. Patients who discontinue study drug for reasons other than relapse or progressive disease (PD) should be followed for assessments of preliminary anticancer activity (Section 8.4) and safety (Section 8.2), if possible.

The primary reason for discontinuation from study drug should be documented on the appropriate eCRF. Patients may discontinue study drug for reasons including but not limited to the following:

- Relapse
- PD
- AE
- Patient decision
- Pregnancy
- Any medical condition that the investigator or sponsor determines may jeopardize the patient's safety if he or she were to continue the study drug
- Use of any concurrent anticancer therapy, including chemotherapy, hormonal therapy, immunotherapy, standard or investigational agents (including Chinese [or other Country] herbal medicine and Chinese [or other Country] patent medicines) for the treatment of cancer [regardless of cancer type])
- Patient noncompliance
 - Study site staff should first counsel patients who are significantly noncompliant (eg, missing 2 treatment cycles) on the importance of study drug compliance and drug accountability. The investigator may, in consultation with the medical monitor, discontinue patients from treatment who are consistently noncompliant.

Treatment with dinutuximab beta should be permanently discontinued if the following toxicities occur:

• Grade 3 or 4 anaphylaxis

- Prolonged Grade 2 peripheral motor neuropathy
- Grade 3 peripheral neuropathy
- Grade 3 vision eye toxicity
- Grade 4 hyponatremia (< 120 mEq/L) despite appropriate fluid management
- Recurrent or Grade 4 capillary leak syndrome (requires ventilator support)

If dinutuximab beta or 13-cis-RA is discontinued permanently before cycle 5 for reasons other than relapse or PD, the other drug could be continued per the study protocol.

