10.2.2. Adverse Events

The AE verbatim descriptions (investigator's description from the eCRF) will be coded using MedDRA. AEs will be coded to MedDRA (version 20.1 or higher) lowest level term, preferred term, and primary system organ class.

A TEAE is defined as an AE that had an onset date or a worsening in severity from baseline (pretreatment) on or after the first dose of study drug(s) and up to 40 days following last dose of study drug or initiation of new anticancer therapy, whichever occurs first.

The incidence of TEAEs will be reported as the number (percentage) of patients with TEAEs by system organ class and preferred term. A patient will be counted only once by the highest severity grade per NCI-CTCAE version 5.0 within a system organ class and preferred term, even if the patient experienced ≥ 1 TEAE within a specific system organ class and preferred term. The number (percentage) of patients with TEAEs will also be summarized by relationship to the study drug(s).

Treatment-related AEs include those events considered by the investigator to be related to study drug or with missing assessment of the causal relationship. SAEs, deaths, ≥ Grade 3 TEAEs, treatment-related TEAEs, and TEAEs that led to treatment discontinuation, treatment interruption, or dose delay will be summarized.

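### The TEAE window can close while 13-cis-RA is still being taken, because protocol 6.3, 7.4 and 7.6.1 do not agree on when other anticancer therapy may start after an early stop of dinutuximab beta

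*Protocol*

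**What the plan says.** **When other therapy is barred.** Protocol 6.3 prohibits "Any chemotherapy, hormonal anticancer therapy, radiotherapy, or experimental" anticancer medication outside the study. The bar lasts until the Safety Follow-up Visit assessments are complete or patients have "discontinued study drug with dinutuximab beta prematurely". Whether 13-cis-RA has also stopped is not mentioned.

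**When one study drug may go on alone.** Protocol 7.6.1: "If dinutuximab beta or 13-cis-RA is discontinued permanently before cycle 5 for reasons other than relapse or PD, the other drug could be continued" under the protocol. SAP 6.3.1 counts both dinutuximab beta and 13-cis-RA as study drugs.

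**What 7.6.1 says about other therapy.** Its list of discontinuation reasons includes "Use of any concurrent anticancer therapy, including chemotherapy, hormonal therapy, immunotherapy, standard or investigational agents". The list is introduced by "Patients may discontinue study drug for reasons including but not limited to the following".

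**Post-study treatment.** Protocol 7.4 allows it after the EOT Visit. For early stoppers that visit falls within 7 days of the decision that study drug must stop permanently. Section 7.4 does not say whether this means one study drug or both.

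**TEAE window.** Protocol 10.2.2 runs it from first dose "up to 40 days following last dose of study drug or initiation of new anticancer therapy, whichever occurs first". SAP 6.6.2 has the same cut-off.

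**AE recording.** Protocol Table 5 also stops recording at new anticancer therapy. The text of 9.5.1 above that table continues to 40 days after the last dose, with no such cut-off.

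**The concern.** Take a patient who stops dinutuximab beta for toxicity and stays on 13-cis-RA. Section 6.3, read literally, no longer bars other anticancer therapy. Section 7.6.1 treats such therapy as a possible reason to stop study drug. Section 7.4 makes post-study treatment depend on an EOT Visit that this patient may or may not have reached.

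If other therapy starts and 13-cis-RA is not stopped, the TEAE definition ends that patient's window while a study drug is still being taken. Neither 10.2.2 nor SAP 6.6.2 requires that dosing has ended first, and neither says which drug's last dose starts the 40 days.

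Safety of the combination is a primary objective, and SAP 6.6 reports related TEAEs separately for the two drugs. Events during later 13-cis-RA dosing would be missing from those tables. If a site follows Table 5, they may not be recorded at all, and then the SAP's listing of all AEs, treatment-emergent or not, cannot recover them.

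**Working it through.** The plan gives no figure for this point, so the check is a reading of the passages followed by a day count.

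**1. Passages side by side, for a patient off dinutuximab beta and still on 13-cis-RA**

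| Section | Other anticancer therapy |
|---|---|
| 6.3 | Can be read as no longer barred |
| 7.4 | Allowed after the EOT Visit; unclear whether that visit is due while 13-cis-RA continues |
| 7.6.1 | A reason for which study drug may be stopped; no stop is required |
| 10.2.2, SAP 6.6.2 | Ends the TEAE window, whether or not a study drug is being taken |
| Table 5 | Ends AE recording |
| 9.5.1 text | Does not end AE reporting |

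**2. Inputs for the day count**

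- Five cycles of 35 days, with 13-cis-RA on Days 12 to 25 of each, so 14 dosing days per cycle (protocol 3.1).
- A 40-day tail after the last dose (protocol 10.2.2).
- About 8 patients (protocol 10.6).
- Assumption: 13-cis-RA keeps its nominal days after dinutuximab beta stops.

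Calendar check against protocol 3.1: 5 × 35 / 7 = 25 weeks of treatment, and 4 + 25 + 6 = 35 weeks in all. Both agree with the stated durations.

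**3. Window without other therapy**

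Last 13-cis-RA day: L = 4 × 35 + 25 = Day 165. Last day of the window: L + 40 = Day 205.

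**4. Window with other therapy**

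Let N be the day on which other therapy starts, counted as the first day outside the window. Under the present rule the last day inside is the smaller of L + 40 and N − 1.

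Suppose the last infusion ends on Day 11 of cycle c and other therapy starts the next day. Then N = (c − 1) × 35 + 12, and the 13-cis-RA dosing days outside the window are 14 × (6 − c).

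| c | N | Dosing days outside | Days N to 165 | Days N to 205 |
|---|---|---|---|---|
| 1 | 12 | 70 | 154 | 194 |
| 2 | 47 | 56 | 119 | 159 |
| 3 | 82 | 42 | 84 | 124 |
| 4 | 117 | 28 | 49 | 89 |

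Cycle 5 is omitted because 7.6.1 speaks of stops before Cycle 5.

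The 70 days are an upper bound. If continuing a drug means that at least one dose has already been taken, the earliest case has a first 13-cis-RA dose on Day 12 and other therapy from Day 13. The bound is then 70 − 1 = 69.

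**5. How often**

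The documents give no rate. One affected patient is 1/8 = 12.5% of the Safety Analysis Set. For an assumed chance p per patient, the probability of at least one case among 8 is 1 − (1 − p)^8: 34% at p = 5%, 57% at 10% and 83% at 20%. These values of p are illustrations only.

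**The case against.** The sections can be read as compatible. Section 6.3 says when other therapy ceases to be barred, and 7.6.1 says that such therapy is a ground for ending study drug. The second drug may go on only under the protocol, which includes that ground. The synopsis likewise gives study drugs until relapse, progression, "unacceptable toxicity, death, or other discontinuation criterion is met". On this reading 13-cis-RA ends when other therapy begins, and only part of the 40-day tail is cut, as the TEAE rule intends. The phrase in 6.3 is also awkward and may mean study treatment as a whole. Much of this stands: it makes the gap less likely. It does not close it, because the 7.6.1 list is permissive and no sentence requires 13-cis-RA to stop.

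A reader might infer that adverse events in this period are simply lost. The documents do not support that. The text of 9.5.1 keeps all AEs reportable to 40 days after the last dose, 3.1 says the same of monitoring, and related SAEs are reportable at any time. What is exposed is the TEAE tables and, if Table 5 is followed, the recording of nonserious AEs and of SAEs judged unrelated.

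Closing the window at new anticancer therapy is a reasonable guard against confounding, and both documents state it. That holds once study drug has ended. It is a weaker reason to discard time on study drug.

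**Conclusion.** The point holds as a conflict of wording with a consequence for a primary safety definition. Sections 6.3, 7.4 and 7.6.1 leave open whether a patient on 13-cis-RA alone may start other therapy, and the TEAE rule then allows the window to close during dosing. Table 5 and the text of 9.5.1 also disagree on recording.

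The size is at most 70 dosing days of 13-cis-RA for one such patient, on the nominal calendar and with other therapy from Cycle 1 Day 12. The pathway is probably uncommon. It excludes stops for relapse or progression, and it needs a patient kept on 13-cis-RA despite a listed reason to stop.

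Three stronger readings are tempting but not supported:

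- That 6.3 plainly lifts the ban. Its wording is ambiguous, and 7.4 and 7.6.1 bear on it.
- That about 95% of the window is lost (194 of 205 days). That is a calendar count, with 84 off-drug days between courses (154 − 70) and the 40-day tail. Starting from an earlier stop, such as Cycle 1 Day 8, adds only days before any 13-cis-RA is due.
- That EFS is also at fault. Censoring at new therapy is prespecified in SAP Table 1 for an exploratory endpoint.

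**What to change.** 1. The sponsor must reconcile protocol 6.3, 7.4 and 7.6.1 on when other anticancer therapy may start after one study drug is stopped. Which clinical rule applies is for the sponsor; none is proposed here.
2. Reconcile Table 5 with the text of 9.5.1 on when AE recording ends.
3. In protocol 10.2.2, Table 5 and SAP 6.6.2, state that new anticancer therapy closes the TEAE and recording window only once the last dose of the last study drug has been given. In the notation above, the last day inside becomes the smaller of L + 40 and the larger of L and N − 1. With N = 12 it moves from Day 11 to Day 165, so all 70 dosing days stay in. If other therapy starts after the last dose, nothing changes.
4. Flag AEs with onset after the start of new anticancer therapy in the listings.

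The cost is a few sentences in the protocol and one in the SAP. The downside is that a few AEs confounded by the new therapy enter the TEAE tables, which matters with about 8 patients; the flag lets a reader set them aside.

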6.4. Medications to Be Used With Caution

Potential interaction between study drug and concomitant medication

No interaction studies have been performed. Monoclonal antibodies (mAbs) are considered to have a low potential for drug-drug interactions with other therapeutic proteins or small molecules, as mAbs are mainly delivered by parenteral administration and are metabolized via the reticuloendothelial system or target-mediated disposition to peptides and amino acids. Therefore, as an intravenous IgG1 mAb, the concern for drug-drug interactions of dinutuximab beta is very low. However, in Study APN311-201, dinutuximab beta induced the release of cytokines, in particularly that of IL-6 and TNFα. Cytokines can affect expression levels of cytochrome P450 (CYP450), and IL-6 is known to decrease the activity of CYP450. A risk for indirect reduction of CYP450 activity may occur due to higher TNFα and IL-6 levels. Therefore, interactions with concomitantly used small molecules metabolized by CYP450, cannot be excluded. Caution should be applied when dinutuximab beta is co-administered with CYP450 substrates with a narrow therapeutic index.

If CYP450 substrates will be used, the medical monitor and clinical pharmacologist should be consulted. Please refer to Drug Development and Drug Interactions: Table of Substrates, Inhibitors and Inducers (FDA 2016) for a complete list of CYP450 substrates.

For 13-cis-RA, detail information could consult the relevant prescribing local label of 13-cis-retinoic acid.

7. STUDY PERIODS, VISITS, OR PROCEDURES

7.1. Screening Period

Screening evaluations will be performed \leq 28 days before the first dose of study drug. A patient who agrees to participate in this study will sign the ICF before undergoing any study-specific screening assessment. Refer to Section 8.1 for instructions regarding screening assessments.

7.1.1. Informed Consent and Screening Log

Voluntary, written informed consent for participation in the study must be obtained before performing any study-specific procedures. ICFs for enrolled patients and for patients who are screened but not enrolled will be maintained at the study site.

The investigator will maintain a screening log to record details of all patients screened and to confirm eligibility or record reasons for screening failure, as applicable.

7.2. Enrollment

Prior to enrollment, the investigator is responsible for assessing and confirming that each patient meets all inclusion eligibility criteria for this study and that none of the exclusion criteria apply. All results from the screening procedures and relevant medical history must be available and reviewed by the investigator before eligibility can be determined. No eligibility waivers will be granted.

Sponsor verification of patient eligibility will be managed by way of source data verification in accordance with International Council for Harmonisation (ICH) E6.

The sponsor's medical monitor will support the investigator and/or site staff by answering any queries or questions relating to protocol eligibility criteria.

7.3. Treatment Period

Patients enrolled by the sponsor will be treated as described in Section 5.2.

Refer to Section 7.6 for additional considerations regarding treatment continuation and withdrawal.

Assessments before the start of dinutuximab beta infusion on Day 1 of each cycle:

- Oxygen-Saturation measurement
- Physical examination including vital signs, height, and weight
- Performance status
- 12-Lead ECG
- Chest X-ray
- Complete blood count including differential count*
- Biochemistry*

- Urinalysis*
- Pregnancy test in WOCBP
- Blood sampling for PK (30 minutes before infusion) in Cycle 1, 2, 3 and 4

*If clinical chemistry, hematology, coagulation and urinalysis at screening are not performed ≤ 7 days before study drug administration on Day 1 of Cycle 1, these tests should be repeated and reviewed before study drug administration. After Day 1 of Cycle 1, results are to be reviewed within 72 hours before study drug administration.

Assessments during dinutuximab beta infusions:

- Performance status (on each infusion day)
- Blood sampling for PK (infusion starting time ±1 hour on Day 3 and Day 8 in Cycle 1)
- The following assessments must be regularly repeated during dinutuximab beta infusions according to routine medical care procedures to ensure safe treatment of the patients:
 - Physical examination including vital signs
 - Complete blood count (including differential count) and biochemistry on Day 8
- Electrocardiography (ECHO) or multigated acquisition scan (MUGA) scan as clinically indicated

On Day 11 of each cycle, evaluations and blood sampling must be done just before the end of dinutuximab beta infusion, ie, within a couple of minutes before the end of infusion. Evaluations must include the following:

- Physical examination including vital signs
- Performance status
- 12-Lead ECG
- Complete blood count (including differential count) and biochemistry
- Blood sampling for PK (5 minutes before the end of infusion) in Cycle 1, 2, 3 and 4

Assessments after dinutuximab beta infusions:

- Complete blood count (including differential count) and biochemistry (Days 15, 22, and 29)
- Blood samples for PK (Day 15 and Day 22 [optional], and Day 29 in Cycle 1)

The guidelines for pain control must be followed strictly for the whole study duration. If a patient has an unacceptable pain-toxicity profile, he/she might need more intense pain treatment such as intravenous morphine after Day 5. If this is the case, in the following cycles, the treatment team should again try to taper intravenous morphine.

AEs and concomitant medications are documented throughout all phases.

